RRMS	Relapsing remitting multiple sclerosis
SAE	Serious adverse event

Study Code: GNC-401
Version No: 3.0
Version Date: 2020-05-01

SAP Statistical analysis plan
SDMT Symbol Digit Modalities Test
SERA Swedish Ethical Review Authority
SOC System Organ Class
SPMS Secondary progressive multiple sclerosis
SUSAR Suspected unexpected serious adverse reaction
TEAE Treatment emergent adverse events
TNF Tumor necrosis factor
T25FW Timed 25-foot walk
ULN Upper limit of normal range
WHO World Health Organization
9-HPT 9-Hole Peg Test

Study Code:	GNC-401
Version No:	3.0
Version Date:	2020-05-01

1. Synopsis

EudraCT number: 2019-004822-15

Title: A Randomized, Double-Blind, Placebo Controlled Trial, Examining the Safety, Tolerability, Pharmacodynamic Effects and Pharmacokinetics of Temelimab Following Rituximab Treatment in Patients with Relapsing Forms of Multiple Sclerosis (RMS)

Study code: GNC-401

Development IIa

Phase:

Short Rationale: Temelimab, a humanised, IgG4-κ monoclonal antibody represents a novel therapeutic approach for degenerative features of Multiple Sclerosis (MS).

Preclinical studies have shown that the envelope protein of the pathogenic human endogenous retrovirus type W (pHERV-W Env) activates microglia into pro-inflammatory phenotype. Furthermore, in the presence of pHERV-W Env, oligodendrocyte precursor cells (OPCs) will not mature into functional oligodendrocytes, thereby preventing optimal remyelination. Temelimab inhibits these effects in preclinical models, both *in vitro* and *in vivo*.

The postulated mode of action of temelimab is to neutralise pHERV-W Env and hence to prevent the pHERV-W Env induced pro-inflammatory activation of microglia, and to preserve OPC maturation. Both these cell types are key cellular targets in neurodegeneration of MS that eventually manifests as disease progression/disability worsening independent of relapse activity and lesion formation. Therefore, temelimab, is expected to address an unmet medical need for patients suffering from MS.

In neuropathological studies, pHERV-W Env was found in chronic active MS lesions, which are considered a main driver of progression in MS and may persist despite current standard disease modifying therapies.

Temelimab has been studied in Phase 2b clinical studies in two-hundred-seventy (270) relapsing-remitting MS (RRMS) patients for up to 96 weeks. In these studies, temelimab showed neuroprotective effects, as documented by:

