- To determine the pharmacodynamic effects of temelimab on neuroprotection and remyelination based on neuroimaging.

Exploratory objectives:

- To assess the clinical and cognitive effects of temelimab (including physical disability)
- To assess the effect of temelimab on quality of life
- To assess the effects of temelimab on exploratory neuroimaging endpoints associated with neuroprotection and remyelination.
- To assess the effects of temelimab on fluid biomarkers associated to myelin integrity, target and immune function
- To determine the PK characteristics of temelimab following repeated IV administration (including CSF distribution) and immunogenicity

Study design:

This is a randomized, double-blind, placebo-controlled Phase IIa clinical study, assessing safety, tolerability, pharmacodynamic effects and pharmacokinetics of temelimab, administered at three different dose levels (18 mg/kg or 36 mg/kg or 54 mg/kg).

The study will consist of a Screening period of a maximum duration of up to 3 weeks (Days -21 to -1) and a treatment period of 48 weeks. On Day 1 all patients who meet eligibility criteria may be randomized (randomization ratio 1:1:1:1) into:

- the placebo group
- the 18 mg/kg group

Study Code: GNC-401
Version No: 3.0
Version Date: 2020-05-01

- the 36 mg/kg group
- the 54 mg/kg group

When the first eight (8), patients randomized into either placebo, 18, 36 or 54 mg/kg group respectively, have achieved ≥ 2 months (8 weeks) of exposure to IMP, formal review by an independent Data Safety Monitoring Board (DSMB) of all of the available safety data from the study will be performed.

The independent DSMB will meet thereafter every 4 months and review all of the available safety data.

All patients will receive double-blind IV infusions of study drug (temelimab 18 mg/kg, 36 mg/kg, 54 mg/kg or matching placebo), via monthly IV infusions for up to Week 44. All patients will be observed for 6 hours following completion of the first administration of IMP infusion and at least 2 hours following completion of the subsequent IMP infusions (second to twelfth). Intra-patient dose escalation of temelimab is not permitted.

Study population: Patients with RMS who have been treated with rituximab for at least 1 year and who meet inclusion/exclusion criteria.

Number of subjects: 40 patients with RMS will be randomized and enrolled (30 temelimab at three dose levels (18, 36 or 54 mg/kg) and 10 placebo)

Inclusion criteria:

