1. The subject has given written informed consent to participate in the study
2. Current diagnosis of RMS, based on the McDonald 2017 criteria¹
3. Having received treatment with rituximab, as per local clinical routine for at least 12 months prior to the Screening Visit
4. Having received their last dose of rituximab not more than 8 weeks and not less than 4 weeks before Randomization (Study Day 1)
5. Having B-cell count $<$ Lower limit of detection (LLOD) ($<0.01 \times 10^{-9}$ CD19⁺ cells/ L)
6. Having expanded disability status scale (EDSS) 2.5 – 5.5 inclusive at Screening
7. Present clinical worsening in one or more neurological domains as assessed by EDSS, ambulatory function as assessed by 6MWT or T25FW, cognitive functioning as assessed by SDMT or increased need of walking aids or pharmacological/procedures for bowel and bladder functions over the last year.
8. Brain Magnetic resonance imaging (MRI), lesion burden with >9 T2 cerebral lesions (assessed within the last 24 months)
9. Stable clinical presentation of MS for 30 days prior to Screening e.g. no relapse, no acute neurological exacerbation.
10. Age range from 18 to 55 years (both inclusive)
11. Body weight between 40 – 100 kg (both ranges are inclusive)
12. No disease modifying therapies (DMTs) other than rituximab, within 12 months of Screening

Study Code:
Version No:
Version Date:

GNC-401
3.0
2020-05-01

13. No contraindication to Biomarker assessments: brain Magnetic resonance imaging (MRI), blood/serum collection and cerebrospinal fluid (CSF) collection
14. Agreeing to undergo two lumbar puncture
15. Be willing and able to follow all study procedures and assessments according to the study protocol
16. Female patients of childbearing potential (FPCBP) or procreative male patients (PMP), willing to use highly effective contraceptive methods throughout the study duration and at least until 5 months after the last study treatment. The investigators must inform the participant about the risks not to use an effective method of birth control during the course of the study and they should discuss with the participant the most appropriate method.
 - FPCBP means female patients who are neither menopausal (for a minimum of at least 2 years), nor underwent irreversible surgical procedures leading to permanent infertility like bilateral tubal occlusion or hysterectomy;

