- The urine dipstick pregnancy test indicates a negative result, but an early pregnancy (\leq 2 weeks from conception) is suspected by the investigator based on anamnestic or clinical elements and cannot be ruled out by further investigations

Investigational product(s), dosage, administration: Temelimumab 18 mg/kg, 36 mg/kg, 54 mg/kg or matching placebo will be given as monthly (4-weekly) intravenous (IV) infusions over 48 weeks (12 administrations in total).

Study endpoints: Primary endpoints:

- Overall Summary of Adverse Events
- AEs by Primary SOC and PT
- SAE by Primary SOC and PT
- Physical Examination: Shift from Baseline to worst post-dose result by Body System
- ECG Interpretation: Change from Baseline to Week 48 and Summary Statistics for change from Baseline to Week 48
- Vital Signs: Summary Statistics For Change From Baseline By Follow-Up Visit

Study Code: GNC-401
Version No: 3.0
Version Date: 2020-05-01

- Concomitant Medications by WHO ATC Level Class 1 and WHO ATC Level Class 2
- Hematology: Normal Range Shifts from Baseline by Follow-Up visit
- Clinical Chemistry (including C-reactive protein): Normal Range Shifts from Baseline by Follow-Up Visit -Safety Set
- Coagulation: Normal Range Shifts from Baseline by Follow-Up Visit - Safety Set
- Urinalysis: Normal Range Shifts from Baseline by Follow-Up Visit

Secondary endpoints:

- Change in magnetization transfer (MTR) in periventricular normal-appearing white matter (NAWM) at week 48 compared to baseline
- Change in magnetization transfer (MTR) in cerebral cortex at week 48 compared to baseline
- Change in T1 lesion volume at week 48 compared to baseline
- Change in T2 lesion volume at week 48 compared to baseline
- Change in brain parenchymal volume fraction at week 48 compared to baseline
- Change in thalamic volume fraction at week 48 compared to baseline

Exploratory endpoints

- An “Overall Disability Response Score” (ODRS) which takes into consideration EDSS, T25FW, dominant and non-dominant 9-HPT, accounting for Worsening and Improvement on Respective Components from Baseline to Week 48
- Event of relapse, as measured by time to relapse and annual relapse rate (ARR)
- Change in Symbol Digit Modalities Test (SDMT) Score at Week 48 compared to Baseline
- Change in Quality of Life (EQ-5D) at Week 48 compared to Baseline.
- Number of new T2 lesions at Week 48
- Change in cortical thickness at week 48 compared to baseline

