- Change in REMyDI myelin fraction in lesions at week 48 compared to baseline
- Change in REMyDI myelin fraction in NAWM at week 48 compared to baseline
- Change in intra-lesional axonal density at week 48 compared to baseline as measured with multi-shell diffusion
- Change in NAWM axonal density at week 48 compared to baseline as measured with multi-shell diffusion
- Change in axonal density, MTR, REMyDI myelin fraction in rim lesions (as part of slowly expanding lesions) vs non-rim lesions at week 48 compared to baseline

Study Code: GNC-401
Version No: 3.0
Version Date: 2020-05-01

- Change in levels of neurofilament-light chain protein (NfL) in serum at Week 48 compared to baseline (Day 1)
- Change in levels of neurofilament-light chain protein in CSF at Week 48 compared to baseline (Day 1)
- Change in levels of proteins or gene expression related to MS or the target of temelimab (pHERV-W ENV), in blood at Week 48 compared to Baseline and in CSF at Week 46 compared to Baseline
- Change in levels of immunoglobulin (Ig) levels in blood (including Total Ig, IgG, IgM, and IgA isotypes) at Week 48 compared to baseline (Day 1)
- Pharmacokinetics (PK) in serum of repeated doses of temelimab at Weeks 4, 24, 46 and 48
- Levels of temelimab in CSF at D15 post last study drug administration (Week 46)
- Antidrug antibodies (ADA) in serum of repeated doses of temelimab at pre dose Day 1, Weeks 4, 24, 46 and 48 (or, in case of early termination, at the study discontinuation visit)

Study period: Q2 2020 (First Patient First Visit)– Q4 2021 (Last Patient Last Visit)

2. Statistics

Statistical analysis will be performed by eXYSTAT SAS. A Statistical Analysis Plan (SAP), and associated templates for Tables, Listings and Figures, will be written and signed before the database lock and study unblinding. These specifications will detail the implementation of all the planned statistical analyses in accordance with the main characteristics stated in this protocol.

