10.2.5.2 Exploratory analyses

Each exploratory endpoint will be described by treatment group in the RS population.

Same Frequentist and Bayesian methodologies will be used.

For frequentist approach change from baseline at Week 48 will be analyzed using a non-parametric ANCOVA including baseline and treatment as factors.

Time to first relapse will be analyzed by Kaplan-Meier method and the associated log-rank test.

For the number of new T2 lesions, each dose will be compared to placebo using a Negative Binomial Generalized Linear Model (NBGLM) studying treatment effect and adjusted for baseline and treatment.

Study Code: GNC-401
 Version No: 3.0
 Version Date: 2020-05-01

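### Week 48 IgG and total Ig may include residual temelimab, itself an IgG, so the planned raw change can be biased upward with dose against placebo

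*Combined protocol and SAP*

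**What the plan says.** - **Endpoint** (1. Synopsis, Exploratory endpoints): "Change in levels of immunoglobulin (Ig) levels in blood (including Total Ig, IgG, IgM, and IgA isotypes) at Week 48 compared to baseline", with baseline given as Day 1. The line does not say that the Day 1 sample is taken before dosing; the anti-drug antibody line in the same list does.
- **Drug** (1. Synopsis, Short Rationale): "Temelimab, a humanised, IgG4-κ monoclonal antibody represents a novel therapeutic approach".
- **Dosing** (1. Synopsis): 18, 36 or 54 mg/kg or placebo, which "will be given as monthly (4-weekly) intravenous (IV) infusions over 48 weeks (12 administrations in total"). The study design paragraph puts the last infusion at Week 44, and section 2.2.3 places the end-of-study visit 4 weeks after the last administration.
- **Drug levels** (1. Synopsis, Exploratory endpoints): "Pharmacokinetics (PK) in serum of repeated doses of temelimab at Weeks 4, 24, 46 and 48". Section 10.2.5.1 plans to derive Cmin and an accumulation factor.
- **Analysis** (section 10.2.5.2): "For frequentist approach change from baseline at Week 48 will be analyzed using a non-parametric ANCOVA including baseline and treatment as factors". The same section carries over the Bayesian methods of section 10.2.4, which report the posterior probability of a negative change in each group and of a positive difference from placebo.
- **Not stated:** the Ig assay, and any handling of study drug within the Ig measurement.

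**The concern.** The study drug belongs to the class of protein being measured. If the assay counts all human IgG, then in each temelimab arm

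measured change in IgG = change in the patient's own IgG + residual temelimab at Week 48.

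The second term is zero on placebo and proportional to dose. Randomisation does not remove it, because treatment causes it. Baseline adjustment does not remove it either, because a pre-dose baseline contains no temelimab.

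The exploratory objectives include immune function, and patients enter after at least 12 months of rituximab with B cells below the limit of detection. A fall in the patient's own IgG is therefore a result this endpoint should be able to show, and the bias acts against showing it. It could also make the drug's own presence look like a dose-ordered rise in IgG. IgM and IgA do not have this problem.

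**Working it through.** **1. Dosing count.** Infusions at Weeks 0, 4, …, 44 number 44/4 + 1 = 12, which matches the protocol's figure. Week 48 is 28 days after the last one.

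**2. Amount infused.** Grams per infusion = mg/kg × kg / 1000. At 70 kg this is 1.26, 2.52 and 3.78 g for 18, 36 and 54 mg/kg. Over the eligible range ("Body weight between 40 – 100 kg") it is 0.72–1.80, 1.44–3.60 and 2.16–5.40 g.

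**3. Residual drug at Week 48.** One compartment, 12 doses:

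C = (dose in g / V) × F, with F = Σ (j = 1 to 12) 2^(−28j / half-life).

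Half-life, volume V and the patient's own IgG are not in the documents. Assumed: 70 kg, V = 3.5, 5 or 6 L, half-life 14 to 30 days (7 days as a low extreme), own IgG 8 g/L. The 30-day value is what results if the 5-month contraception period stands for about five half-lives, a link the documents do not make.

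F = 0.067, 0.333, 0.658 and 1.099 for half-lives of 7, 14, 21 and 30 days.

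| Dose | Low (6 L, 14 d) | Middle (5 L, 21 d) | 5 L, 30 d | High (3.5 L, 30 d) |
|---|---|---|---|---|
| 18 mg/kg | 0.07 g/L | 0.17 | 0.28 | 0.40 |
| 36 mg/kg | 0.14 | 0.33 | 0.55 | 0.79 |
| 54 mg/kg | 0.21 | 0.50 | 0.83 | 1.19 |

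Example: 3.78 g / 5 L × 0.658 = 0.50 g/L.

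As a share of 8 g/L, the range runs from 0.07/8 = 0.9% to 1.19/8 = 14.8%. With a 7-day half-life, the largest value is 3.78/3.5 × 0.067 = 0.07 g/L, under 1%.

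**4. What could be masked.** A 10% loss of own IgG is 0.8 g/L. At 54 mg/kg this is covered at 30 days with 5 L (0.83) or 3.5 L (1.19), but not at 21 days even with 3.5 L (3.78/3.5 × 0.658 = 0.71). At 36 mg/kg it is just about reached at the extreme corner (0.79). At 18 mg/kg the most that can be offset is 0.40/8 = 5%. In the middle case, 54 mg/kg offsets 0.50/8 = 6%.

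**5. Effect on the reported posterior.** Take an artefact of 0.50 g/L, no true change, 10 patients per arm, and an assumed SD of change of 0.8 g/L. The SE of the difference is 0.8 × √(2/10) = 0.36. With a flat prior and a normal approximation, an observed difference equal to the artefact gives P(difference > 0) = Φ(0.50/0.36) ≈ 0.92. For an SD of 0.5 or 1.2 g/L it is about 0.99 or 0.82. These SDs are assumptions too.

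**The case against.** **Silence on the assay.** The text names no Ig assay, and section 2 promises a separate SAP that will detail implementation. An assay that does not register temelimab, or a correction written later, would remove the problem. This stands, so the bias is conditional. It does not dispose of the point: the analysis rule that is stated works on the raw change, and nothing stated protects it.

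**Size.** Every figure beyond the grams infused rests on assumed PK values. This also stands. A reader might infer that a 10% loss of own IgG would generally be hidden. The working does not support that: it needs the top of the range at 36–54 mg/kg and does not occur at 18 mg/kg.

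**Consequence.** A reader might also infer that the trial's development decision or its primary safety conclusions are compromised. The documents do not support this. All inferential analyses are declared exploratory (section 2.2.1). The 80% posterior mark in section 10.2.4 is introduced for lesion volume; the probabilities are extended to other measures, but no Ig-based decision is stated. The listed primary endpoints do not include this one.

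**Baseline.** Day 1 cannot be called drug-free on the text alone, since the Ig line does not say pre-dose. Rituximab given 4 to 8 weeks earlier may also be present. Assuming 0.5–1 g, 4.9 L (70 kg × 0.07 L/kg) and a half-life of 14–28 days, that is about 0.01 g/L (0.5 × 0.0625/4.9) to 0.10 g/L (1 × 0.5/4.9). It applies to all arms and should largely cancel against placebo.

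**Conclusion.** The concern holds in conditional form. If the Ig assay detects temelimab, the planned IgG and total Ig comparisons with placebo are biased upward in dose order. The direction follows from the documents; the size does not. Under the stated assumptions it is modest: about 1–5% of an 8 g/L IgG at 18 mg/kg, 2–10% at 36 mg/kg and 3–15% at 54 mg/kg. It is negligible if the half-life is near 7 days. That is enough to mask a modest fall in own IgG or to suggest a dose-related rise, but not to hide a large fall. Because the endpoint is exploratory, this should be corrected in the SAP but does not threaten the trial's main conclusions.

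**What to change.** In the SAP, before database lock and unblinding:

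1. State that the Day 1 Ig sample is pre-dose.
2. For IgG and total Ig, analyse the change after subtracting the serum temelimab concentration measured at the same Week 48 visit, taken as zero on placebo and at baseline. Show the uncorrected change alongside. Apply this to both the ANCOVA and the Bayesian analyses.
3. Omit the subtraction only if the assay is shown not to detect temelimab.
4. Leave IgM and IgA as planned.

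**Cost.** A few sentences and one subtraction, with no new visit or PK measurement. The corrected value carries PK assay error. It also assumes that the PK assay reports total drug on the same mass scale as the Ig assay, which the documents do not confirm and which anti-drug antibodies could disturb. They also place the PK measurement at the same visit, not necessarily in the same sample. These are reasons to keep the uncorrected result in view.

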2.1. Analysis population

Randomized Set (RS): All patients to whom a therapeutic treatment was randomly assigned using IRS. Patients will be analyzed in their randomization group whatever the treatment they received

Safety Set (SS): All patients having taken at least one dose of IMP. Patients will be affected to the group of treatment they received.

2.2. Statistical methods

2.2.1. General considerations

The following descriptive statistics will be provided depending on the nature of considered data:

- **Qualitative data:** number of observed values, number and percentage of patients per class;
- **Quantitative data:** number of observed values, mean and standard deviation, median, first and

Study Code: GNC-401
Version No: 3.0
Version Date: 2020-05-01

third quartiles, minimum and maximum;

- **Survival data (time to event occurrence or to censoring):** total number of patients, total number and percentage of patients having an event, number of patients at risk, number of patients with censored data, number of patients with event of interest.

The type I error will be set at $\alpha = 5\%$ two-sided.

The treatment effect (temelimab versus placebo) will be estimated as well as its precision: estimate of the difference, standard error (SE) of the estimate and two-sided 95% confidence interval (CI) of the estimate.

In case of formal comparison between treatment groups, the two-sided p-value associated with the treatment effect will also be provided.

All inferential analyses are considered as exploratory in order to have a first estimation of treatment effect. Consequently, no method to handle with multiplicity issues is needed.

2.2.2. Study patients:

Demographic data and other baseline characteristics will be described by treatment group, to assess their comparability, and overall in the RS population. The main patients' characteristics will also be described for SS population.

Disposition of patients, including reasons for withdrawal, protocol deviations, extent of exposure and treatment compliance, as well as concomitant treatments will be described in the RS population.

2.2.3. Safety analysis

Safety and tolerability of temelimab and placebo will be assessed in each treatment group in the safety population.

AE summaries will include all AEs starting on or after study day 1 (i.e. on the day of or following the day of first study treatment administration) and starting before the end of study visit, i.e. 4 weeks after the date of last study treatment administration.

A Summary of AEs (number and % of patients, number of AEs) and summarized by System Organ Class (SOC) and Preferred Term (PT) will be tabulated by treatment group and overall for patients with:

- at least one treatment-emergent adverse event (TEAE),
- at least one related treatment-emergent adverse event (TEAE),
- at least one severe treatment-emergent adverse event (TEAE),
- at least one severe related treatment-emergent adverse event (TEAE),
- at least one serious TEAE,
- at least one serious TEAE related to the study treatment,
- a TEAE leading to treatment discontinuation,
- a related TEAE leading to treatment discontinuation,
- a TEAE leading to death.

Study Code: GNC-401
Version No: 3.0
Version Date: 2020-05-01

AEs will be summarized by presenting the number and percentage of patients having at least one AE and by number of AEs, overall and by treatment group. Data will be presented by SOC and PT using the latest version of MedDRA. A patient with multiple occurrences of the same PT will be counted only once in the AE category.

Separate AE summaries will be presented by SOC, PT, and severity. In the summaries presented by severity, all AEs will be pooled. Specific tables will summarize related AEs to temelimab.

Written narratives will be produced for all SAEs.

Adverse events/SAEs occurring after signing the Inform Consent Form (ICF) but before starting study treatment, including those observed in patients included but never treated with the IMP, will be listed separately from those occurring after treatment start.

Adverse events/SAEs occurring after 4 weeks after the date of last study treatment administration will be also listed separately.

Laboratory data analysis:

The summaries will include all laboratory assessments collected during the study.

All laboratory values will be converted into SI units and will have a severity grade calculated using appropriate common terminology criteria for AEs (NCI CTCAE, version 4.03). A listing of laboratory values will be provided by laboratory parameter and by patient. A separate listing will display notable laboratory abnormalities (i.e. newly occurring CTCAE Grade 3 or 4 laboratory toxicities). The frequency of these notable laboratory abnormalities will be displayed by parameter.

Shift tables using CTCAE grades to compare baseline to the worst post-baseline value will be produced for all relevant safety measures as described in the statistical analysis plan. Note that for parameters with two directions abnormalities (hypo/hyper), two tables will be presented.

The shift tables using Normal Range Shifts from Baseline will be also produced for all safety measures as described in the section 4.3.

Vital signs and physical examination

Vital signs and physical examination will be described, in terms of value at baseline, value at each post-baseline visit; as well as in terms of change from baseline to each post baseline visit. For physical Examination: Shift from Baseline to Worst Post dose Result by Body System will be provided.

Other safety data

Other safety data (e.g. 12-lead electrocardiogram, concomitant medication use) will be listed, notable values will be flagged, and any other information collected will be listed as appropriate. Any statistical procedures performed in order to explore the data will be used only to highlight any comparisons that may warrant further consideration. Change from Baseline by Follow-Up Visit and Summary Statistics for Change from Baseline By Follow-Up Visit will be provided.

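### AE tables select events by start date alone, so an AE that begins before the first infusion and worsens on treatment goes uncounted unless the worsening is recorded as a new event

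*Combined protocol and SAP*

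**What the plan says.** Section 2.2.3 (Safety analysis) sets both limits of the AE window by onset. The lower limit is "AE summaries will include all AEs starting on or after study day 1". The upper limit is "starting before the end of study visit, i.e. 4 weeks after the date of last study treatment administration". The section then lists nine rows of treatment-emergent events: any, related, severe, severe and related, serious, serious and related, leading to discontinuation, related and leading to discontinuation, and leading to death. The abbreviation TEAE is expanded in the abbreviation list, but the text reviewed does not define the term.

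For the period before dosing, the same section says that "Adverse events/SAEs occurring after signing the Inform Consent Form (ICF) but before starting study treatment" "will be listed separately from those occurring after treatment start". It does not say what happens when such an event continues and becomes worse after the first infusion. It counts a patient once for repeated occurrences of a preferred term, without saying at which severity.

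The Synopsis (Study endpoints) places "Overall Summary of Adverse Events" first among the primary endpoints, followed by AEs and SAEs by SOC and PT. Other entries compare with baseline, for example "Physical Examination: Shift from Baseline to worst post-dose result by Body System". The laboratory part of Section 2.2.3 adds "Shift tables using CTCAE grades to compare baseline to the worst post-baseline value".

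**The concern.** A treatment-emergent definition normally has two limbs: events that are new after dosing, and events that were present before dosing and got worse. Section 2.2.3 has only the first. The plan measures against baseline for laboratory values and physical examination, but it has no equivalent for reported AEs.

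Safety and tolerability is the only primary objective, and Section 2.3 relies on comparing the severity and frequency of AEs between doses. If temelimab aggravates a complaint that was already present at the first infusion, that harm is missed in the rows meant to show it. A pre-dose AE that becomes severe, is judged related, or ends treatment would appear only in the pre-treatment listing.

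**Working it through.** No figure in the plan needs reproducing. The check is a reading of the rule, followed by simple arithmetic on its effect.

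**Step 1: apply the rule to one event.** Take an AE that starts within the screening period (Days -21 to -1, Synopsis, Study design), continues past Day 1, and becomes severe before the end of study visit.

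- *One record, original start date kept.* The start date is before Day 1, so the event fails the lower limit. It goes to the pre-treatment listing and counts in none of the nine rows.
- *Worsening entered as a new AE.* The new start date is after Day 1 and before the end of study visit, so the event passes both limits and counts in the severe row, and in the related or discontinuation rows if they apply.

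The same clinical course gives two different tables. The text reviewed does not say which recording convention applies, so the result depends on an unstated choice.

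**Step 2: the boundary on Day 1.** The lower limit is a calendar day, while the separate listing is defined by the start of treatment. An AE that begins on Day 1 before the infusion meets both conditions. This is a second sign that the boundary needs one definition.

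**Step 3: which primary endpoints are affected.** The Synopsis lists 11: overall AE summary, AEs by SOC/PT, SAEs by SOC/PT, physical examination, ECG, vital signs, concomitant medication, haematology, clinical chemistry, coagulation and urinalysis. The first three depend on the AE selection rule, so 3 of 11.

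**Step 4: what the rest of the plan would still show.**

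- Laboratory worsening: CTCAE and normal-range shift tables.
- Examination findings: shift to the worst post-dose result.
- Worsening that becomes serious: a narrative, since these are promised for all SAEs with no limit on start date. It would still be missing from the serious TEAE row.
- Non-serious symptomatic worsening: no table. This includes severe, related or discontinuation-causing events.

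**Step 5: effect of one patient.** Inputs from the Synopsis: 40 patients, 10 per arm, 30 on temelimab.

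- One arm: 1/10 = 10 percentage points.
- All temelimab: 1/30 = 3.3 points.
- All patients: 1/40 = 2.5 points.

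**Step 6: how often this might arise (assumption).** The document gives no rate. Let p be the assumed proportion of patients with a pre-dose AE that worsens on treatment and is not re-entered. The chance of at least one such patient in an arm of 10 is 1 - (1 - p)^10, and the expected number in the trial is 40p.

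- p = 5%: 1 - 0.95^10 = 40%; 40 x 0.05 = 2 patients.
- p = 10%: 1 - 0.90^10 = 65%; 40 x 0.10 = 4 patients.
- p = 20%: 1 - 0.80^10 = 89%; 40 x 0.20 = 8 patients.

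These values are illustrative. Screening lasts at most 3 weeks, so the true rate could lie below this range.

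**The case against.** The strongest objection is that exclusion follows only if a worsening keeps its original start date. If sites enter it as a new AE, the existing sentence already works. The text reviewed is a synopsis and a statistics section: its numbering jumps from 2.2.3 to 10.2.4, and it refers to a section 4.3 that is not in it. A recording rule may exist elsewhere, and Section 2 leaves implementation to an SAP to be signed before database lock. This stands as a limit on the claim. It does not remove the point, because the rule as written gives the wrong count under one ordinary recording convention and nothing in the text excludes that convention.

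A reader might infer that any long-standing condition that worsens on treatment, including MS symptoms present at entry, is left out of every treatment-emergent table. The document does not support that. The separate listing covers AEs occurring after consent, and nothing says that a symptom predating consent is an AE with an early start date. Its aggravation may itself be the AE that starts on treatment. Inclusion criterion 7 does require worsening over the last year, but criterion 9 also requires a stable presentation for 30 days before Screening. MS worsening is also measured through the ODRS, relapse and SDMT.

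A reader might also infer that the primary endpoint as a whole is compromised, or that the rule favours temelimab. Only 3 of 11 primary endpoints depend on the rule, and the rule is the same in every arm of a blinded trial. It would hide a difference only to the extent that worsening of pre-dose events is more common on temelimab, and the document gives no evidence on that. The safety evaluation is descriptive, so no test or decision threshold changes. Pre-dose events are still listed, and the DSMB reviews the available safety data.

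**Conclusion.** The point holds in a limited form. Section 2.2.3 selects AEs by start date alone, and neither a TEAE definition nor a worsening clause appears in the text reviewed. An AE that begins between consent and the first infusion and worsens on treatment is not counted in the TEAE, severe, related, serious or discontinuation rows unless the worsening is recorded as a new AE. After allowing for the shift tables and SAE narratives, the uncovered part is mainly non-serious symptomatic worsening, which bears directly on tolerability.

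Each affected patient moves a row by 10 points in one arm or by 3.3 points across temelimab. How many patients would be affected cannot be derived from the document. The conclusion assumes that no recording rule for worsening exists in parts of the protocol outside the text reviewed; if one does, the remaining need is to state the definition in the SAP.

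**What to change.** In the SAP, define a TEAE as an AE that starts, or increases in severity or becomes serious, from the start of the first infusion to 4 weeks after the last. Count it at its worst on-treatment grade. In the eCRF completion instructions, state that worsening of a pre-dose event is recorded as a new AE line dated at the change, or as a dated severity change on the existing line. Anchoring the window to the start of the infusion also settles the Day 1 overlap.

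If patients are already enrolled, review ongoing pre-dose AEs for dated severity changes before unblinding.

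The cost is one SAP sentence, one eCRF instruction and slightly higher AE counts. Sample size and visit schedule do not change.
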